1.3.3.2 Preliminary PK analysis

Dose escalation will be guided by preliminary PK analysis with the following aims:

- Ascertaining that adequate exposures are reached in this trial as a basis for further development of BI 474121,
- Ascertaining that the expected gMean exposure values of the next dose group do not exceed the maximum acceptable exposure in order to protect subjects' safety, and
- Ascertaining that dose escalation is stopped in case observed exposure values of a single subject exceed the maximum acceptable exposure.

For details, see Sections [3.3.4.3](#) and 7.4.

1.3.4 Dose selection for food effect study (BA part)

BI 474121 has not been administered to humans. Due to this very early stage of clinical development it remains open which dose will correspond with a therapeutic dose in patients. Therefore two optional dose levels (2.5 mg or 10 mg) are planned for the BA part with the aim to select the highest possible dose strength. A dose of 2.5 mg to be used in the BA part requires that an at least 4-fold higher dose of the SRD part (i.e. at least 10 mg) shows acceptable safety and tolerability. A dose of 10 mg to be used in the BA part requires that in the SRD part the maximum dose of 40 mg shows acceptable safety and tolerability.

1.4 BENEFIT - RISK ASSESSMENT

1.4.1 Expected benefit for the target population

Participation in this clinical trial is without any (therapeutic) benefit for healthy subjects. Their participation, however, is of major importance for the development of BI 474121 as treatment for CIAS as well as for symptomatic treatment of mild to moderate AD.

Subjects are exposed to risks of study procedures and risks related to the exposure to the trial medication.

1.4.2 Procedure-related risks

[figure not shown]
The use of an indwelling venous catheter or venepuncture for e.g. blood sampling may result in mild bruising, syncope, and, in rare cases, in transient inflammation of the wall of the vein, or nerve injury, potentially resulting in paraesthesia, reduced sensibility, and/or pain for an indefinite period.

The total volume of blood withdrawn per subject during the entire study will not exceed the volume of a normal blood donation (500 mL). No health-related risk to healthy subjects is expected from withdrawal of this volume of blood.

1.4.3 Drug-related risks and safety measures

Factors of risk may derive from particular knowledge or the lack thereof, regarding (1) the mode of action, (2) the nature of the target, (3) the relevance of animal models and/or (4) findings in non-clinical safety studies.

Safety measures

The following safety measures will be applied in order to minimise the risk for healthy volunteers:

- Dose selection is based on a sound preclinical package including 4-week toxicological studies (see Section [1.2.3](#)) and non-clinical pharmacology data (Section [1.2.1](#)).

Proprietary confidential information © 2020 Boehringer Ingelheim International GmbH or one or more of its affiliated companies

- Careful selection of starting dose in the SRD part of the trial as described in Section [1.3](#).
- Dose escalation in the SRD part of the trial will be shallow with an increase of no more than 2-fold beyond the predicted human therapeutic dose of 2.5 mg of BI 474121.
- Measurement of BI 474121 plasma concentrations and preliminary determination of PK parameters in the SRD part of the trial (C_{max} , AUC_{0-24} , see Section [7.3.4](#)). For precautionary reasons, drug plasma concentrations in this healthy volunteer trial will not exceed the geometric mean (gMean) C_{max} of 657 nM for C_{max} and 6,201 nM*h for AUC_{0-24} (see Section [2.1](#)). Dose escalation will be stopped if the C_{max} or AUC_{0-24} of at least 1 subject of one dose group exceeds or if the estimated systemic exposure (group gMean values) of the next dose level is expected to exceed the maximum acceptable exposure (see Section 7.3.4).
- For safety reasons, each dose group of 8 subjects (6 on active, 2 on placebo) in the SRD part of the trial will be divided in three cohorts with staggered inclusion of subjects (see Section [3.1](#) for details). The first drug administration of cohort 2 and the first drug administration of cohort 3 will be no earlier than 22 hours after first drug administration in the previous cohort. Within each cohort, drug administrations will be separated by at least 10 min. This design ensures that between first and second active dose of each dose level there is a time interval of at least 22 hours. This time interval is expected to be sufficient to detect relevant first acute effects of BI 474121. In the BA part of the trial, 12 subjects will be dosed in one cohort with no minimum time interval defined between dosing.
- An extensive safety laboratory will be performed in both trial parts (see Section [5.2.3](#)). This will also include sensitive serum markers to early detect skeletal muscle injury.
- A ECG monitoring up to Day 5 (96 h post dose in the SRD part of the trial) will be performed to cover the anticipated period of highest drug exposure. Continuous ECG measurement will be performed over 4 hours post dose in the SRD part of the trial. Dose escalation in the SRD part of the trial would be stopped as soon as at least 2 subjects at one dose level showed relevant QT prolongation (see Section [3.3.4.2](#) for details).
- In the SRD part of the trial, orthostatic testing will be performed prior to and following study drug administration at the time points indicated in the [Flow Chart](#) to assess hemodynamic effects of BI 474121. Dose escalation will be stopped if clinical symptoms will be observed in more than 1 subject (severe) or more than 3 subjects (moderate) in one dose group.
- Only if the respective dose of BI 474121 was safe and showed acceptable tolerability and if no stopping criterion was met (see Section 3.3.4.2), the next higher dose will be given not earlier than 7 days (up to dose group 3) or 14 days (from dose group 4 onwards) after first dosing of the previous dose group (referring to the 1st subject of each respective dose group) in the SRD part of the trial. A documented Safety Review must take place prior to each dose escalation (see Section 3.1).

Proprietary confidential information © 2020 Boehringer Ingelheim International GmbH or one or more of its affiliated companies

- The subjects will stay at the trial site for at least 48 hours after study drug administration in the SRD part of the trial and for at least 24 hours after study drug administration in the BA part of the trial. Based on an anticipated half-life of BI 474121 of 18.6 hours, this is expected to cover the period of highest risk / peak effect.
- During in-house confinement, the subjects will be under medical observation and thoroughly monitored for both expected and unexpected adverse events.

Conclusion

In summary, although not tested in humans to date, BI 474121 has the potential to become an oral treatment for cognitive deficits in patients with schizophrenia and AD, both indications with a large medical need.

Based upon preclinical data for BI 474121 as well as the implemented safety measures described above, healthy subjects will not be exposed to undue risks in relation to the important information expected from this trial as a basis for further clinical development of this compound.

Healthy volunteers are not expected to have any direct benefit from participation in this FIH clinical trial with BI 474121. Considering the medical need for an effective treatment in schizophrenia and AD, the sponsor considers that the benefit outweighs the potential risks and justifies exposure of healthy human volunteers.

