The dose groups will be dosed consecutively in ascending order, and a time interval of at least 3 days will be maintained between the last drug administration to subjects in the previous dose group and the first drug administration to subjects in the subsequent dose group. Moreover, a time interval of at least 7 days will be maintained for DG 1 to 3 and 14 days for DG 4 to 7 between the first drug administration to subjects in the previous dose group and the first drug administration to subjects in the subsequent dose group. The decision to treat the next dose group will be based upon safety, tolerability and pharmacokinetic data (for details refer to Section [7.4](#)) of the preceding dose groups. The next dose group will only be treated if, in the opinion of the investigator, no safety concerns have arisen in the preceding dose groups (i.e. no dose-limiting events occurred), and if none of the pre-specified trial-specific stopping criteria have been met (refer to Section [3.3.4.2](#)).

A documented safety review must take place prior to each dose escalation. Furthermore, an unscheduled safety review meeting can be requested anytime by the Principal Investigator (or an authorised deputy) or the sponsor of the study (for instance, due to the occurrence of any unforeseen adverse events).

Although no formal Safety Review meeting will take place within a given dose group, safety will be continuously monitored during this trial, and an individual will only be dosed in the absence of any safety concern (i.e. no dose-limiting events occurred) and if none of the pre-specified trial-specific stopping criteria have been met (refer to Section 3.3.4.2).

At minimum, data from 4 subjects on active drug need to be available for escalation to a higher dose. For the minimum dataset with regards to preliminary PK data, see Section 7.4. The minimum data set for review consists of the following:

- AEs in the current and preceding dose groups up to at least 48 h post dosing, including clinically relevant findings from ancillary safety testing listed below (Note: AEs may be ongoing at the time of Safety Reviews and AE information may be subject to change prior to Database Lock)
- Results from 12-lead ECG and continuous ECG monitoring in the current and preceding dose groups up to at least 24 h (DG 1 to 3) or 48 h (DG 4 to 7) post dosing
- Vital signs and results from the orthostatic tests in the current and preceding dose groups up to at least 24 h post dosing

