- Clinical laboratory tests in the current and preceding dose groups up to 24 h post dosing
- Preliminary PK data for the selected time as per Section 7.4

- Check of criteria for stopping subject treatment as per Section [3.3.4.1](#)

The decision to escalate the dose will be made jointly by the Principal Investigator (or an authorised deputy) and the Clinical Trial Leader (or an authorised deputy) after in-depth analysis of all available safety data, especially SAEs (if occurred), AEs, and out-of-range laboratory results (if considered clinically significant). In addition and depending on the results and findings, suitable experts from the sponsor or external institutions may be consulted on an as needed basis. In these cases expert recommendations will be documented in the minutes of the Safety Review and considered for the decision making. Dose escalation will only be permitted if no safety concerns exist neither in the opinion of the Principal Investigator (or an authorised deputy) nor the Clinical Trial Leader (or an authorised deputy).

Safety Reviews can be conducted face-to-face or by video/telephone conference. The Clinical Trial Leader is responsible for the organisation and minutes of the reviews. Minutes will be signed off by the Principal Investigator (or an authorised deputy) and Clinical Trial Lead (or an authorised deputy), and will be filed in the ISF and TMF.

BA part

The BA part will be performed as randomised, open-label, three-way, six-sequence, cross-over trial in healthy male subjects in order to assess (1) the relative bioavailability of the tablet relative to PfOS (both administered under fasted conditions) and (2) the relative bioavailability of the tablet administered under fed and fasted conditions. The subjects will be randomly allocated to the 6 treatment sequences. The treatments will be one 2.5 mg or one 10 mg tablet administered in the fasting and fed state, after a standardised high-fat, high-calorie breakfast, as well as 2.5 mg or 10 mg PfOS administered in the fasting state. For details refer to Section [4.1.4](#).

There will be a wash out period of at least 7 days between the treatments.

A total of 12 healthy male subjects is planned to participate in the BA part.

An overview of all relevant activities is provided in the [Flow Chart](#). For visit schedule and details of trial procedures at selected visits, refer to Sections [6.1](#) and [6.2](#), respectively.

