3.3.4.3 Discontinuation of the trial by the sponsor

Boehringer Ingelheim reserves the right to discontinue the trial at any time for any of the following reasons (#5, #6 and #7 mandatory discontinuation criteria) :

1. Failure to meet expected enrolment goals overall or at a particular trial site
2. New toxicological findings, serious adverse events, or any safety information invalidating the earlier positive benefit-risk assessment.
3. Violation of GCP, or the CTP impairing the appropriate conduct of the trial.
4. The sponsor decides to discontinue the further development of the investigational product
5. Dose escalation in the SRD part or treatment in the BA part will be stopped if at least 2 subjects on active treatment at one dose level (SRD part) or 2 subjects in the BA part have relevant individual QT prolongations, i.e. a QTc increase of greater than 60 ms from baseline and/or an absolute QT or QTc greater than 500 ms, as confirmed by a repeat ECG recording.
6. Dose escalation in the SRD part will be stopped, if the C_{max} or AUC_{0-24} of at least 1 subject of one dose group increases above the following exposure thresholds or if the estimated gMean exposure is expected to exceed a C_{max} of 657 nM or an AUC_{0-24} of 6,201 nM*h. In this case, one or two additional dose levels lower than the planned next dose level may be given, as long as the expected gMean exposure values of the interim dose do not exceed these exposure thresholds. Estimation will be done based on preliminary PK results of preceding dose groups (see Section [7.4](#))
7. Occurrence of severe non-serious adverse events considered as drug-related by the investigator in 2 subjects of the same dose group (8 subjects) in the SRD part, or 3 subjects of the BA group (12 subjects), or occurrence of at least one drug-related serious adverse event. Moreover, dose escalation in the SRD part will be terminated if more than 3 of the actively dosed subjects at one dose level show drug-related and clinically relevant adverse events of at least moderate intensity.

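### Section 1.4.3 promises an orthostatic stop to SRD dose escalation that is absent from the mandatory criteria in Section 3.3.4.3, and criterion #7 covers it only in part

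*Protocol*

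**What the plan says.** Protocol Section 1.4.3 lists the safety measures for the SRD part. The bullet on orthostatic testing commits to halting escalation when "clinical symptoms will be observed in more than 1 subject (severe) or more than 3 subjects (moderate) in one dose group". It does not restrict the count to subjects on active drug or to events judged drug-related.

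Section 3.3.4.3 lists seven grounds for discontinuation by the sponsor, three of them binding (#"5, #6 and #7 mandatory discontinuation criteria"). Criterion #5 is QT prolongation, #6 is exposure and #7 is adverse events. None mentions orthostatic tests or symptoms. Two parts of #7 come close:

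- Severe events: "Occurrence of severe non-serious adverse events considered as drug-related by the investigator in 2 subjects of the same dose group (8 subjects").
- Moderate events: escalation ends when "more than 3 of the actively dosed subjects at one dose level show drug-related and clinically relevant adverse events of at least moderate intensity".

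Section 3.1 allows the next dose group only if the investigator has no safety concern and "none of the pre-specified trial-specific stopping criteria have been met". For those criteria it refers to Section 3.3.4.2, which deals with withdrawal of consent and contains no stopping criteria.

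**The concern.** Section 1.4.3 contains three specific escalation stops: exposure, QT and orthostatic symptoms. The first two have counterparts in the mandatory list (#6 and #5). The third has none, and its bullet gives no cross-reference. Yet the benefit-risk conclusion at the end of 1.4.3 relies on the safety measures described there, and this is one of them.

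Criterion #7 does not replace it. Section 5.2.3 records orthostatic symptoms as adverse events, so some of them count under #7, but only after a relatedness judgement. That judgement is made by an investigator who knows who received placebo (Section 4.1.5.1). A placebo subject's symptoms are therefore unlikely to be called drug-related, although 1.4.3 as written counts them.

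At stake is whether the people holding a safety review in a first-in-human trial can tell from the protocol which orthostatic count binds them. Section 3.1 puts the orthostatic results in the minimum data set for that review, but the mandatory list has no orthostatic criterion to apply to them.

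**Working it through.** **Inputs.** Section 3.1 gives 6 active and 2 placebo subjects per dose group, and 7 × (6 + 2) = 56, which agrees with the planned SRD total. The protocol states no operating characteristics for either rule, so there is no probability to reproduce.

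**The two rules side by side**

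| | Section 1.4.3, orthostatic bullet | Section 3.3.4.3, criterion #7 |
|---|---|---|
| Severe: number | more than 1 | 2 |
| Severe: who | dose group (8) | dose group (8) |
| Severe: which events | orthostatic symptoms | drug-related, non-serious |
| Moderate: number | more than 3 | more than 3 |
| Moderate: who | dose group (8) | actively dosed (6) |
| Moderate: which events | orthostatic symptoms | "drug-related and clinically relevant adverse events of at least moderate intensity" |

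The severe counts use the same number and the same group, and differ only in which events qualify. The moderate counts differ in both subjects and events.

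**Patterns on which the rules differ**, looking at orthostatic events only and taking placebo events as not drug-related:

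- 3 active + 1 placebo, all moderate: 1.4.3 counts 4 > 3 and is met; #7 counts 3 and is not.
- 4 active moderate, one judged unrelated: 1.4.3 counts 4 and is met; #7 counts 3 and is not.
- 2 severe, one on placebo or judged unrelated: 1.4.3 counts 2 > 1 and is met; #7 counts 1 and is not.
- 3 moderate + 1 severe, all active and related: #7 counts 4 of at least moderate intensity and is met. Section 1.4.3 read literally has 1 severe (not more than 1) and 3 moderate (not more than 3), and is not met.

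Enumerating all 1,260 count patterns in a 6 + 2 group gives 648 that meet only 1.4.3 and 1 that meets only #7 (the last example). If *moderate* in 1.4.3 means at least moderate, the figures are 672 and 0. These counts are unweighted and are not probabilities.

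**Probability for the moderate count.** The symptom rates are assumptions, because the documents give none. Let X ~ Bin(6, a) be active cases, all judged related and clinically relevant, and Y ~ Bin(2, b) placebo cases, with no severe cases. Then

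- P(#7 met) = P(X ≥ 4)
- P(1.4.3 met) = P(X ≥ 4) + P(X = 3)·P(Y ≥ 1) + P(X = 2)·P(Y = 2)

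At a = 40%: P(X ≥ 4) = 0.1792, P(X = 3) = 0.27648, P(X = 2) = 0.31104.

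| Placebo rate b | P(Y ≥ 1) | P(Y = 2) | 1.4.3 met | #7 met |
|---|---|---|---|---|
| 40% | 0.64 | 0.16 | 0.1792 + 0.1769 + 0.0498 = 0.406 | 0.179 |
| 5% | 0.0975 | 0.0025 | 0.1792 + 0.0270 + 0.0008 = 0.207 | 0.179 |
| 0% | 0 | 0 | 0.179 | 0.179 |

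With equal rates in both arms at 20% and 30%, the figures are 0.056 against 0.017 and 0.194 against 0.071. Any active case judged unrelated lowers the #7 probability and leaves the 1.4.3 probability unchanged.

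**References.** Section 3.3.4.2 is cited for stopping criteria twice in 1.4.3 (the QT bullet and the bullet on the next higher dose) and twice in 3.1 (the gate to the next group and dosing within a group). Section 1.3.3.2 cites 3.3.4.3, which does hold them.

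**The case against.** The strongest reply is that stopping rules add to one another. Section 1.4.3 is protocol text and says escalation will be stopped. Criterion #7 nowhere says escalation may continue when its own count is not reached. Read together, either rule stops escalation. This stands as a reasonable reading, so a reader who infers that the two passages yield opposite escalation decisions goes further than the text. What remains is that the protocol does not state this reading, and the gate sends reviewers to a section with no criteria.

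The orthostatic bullet may also be loose shorthand for #7. The numbers match, and the QT bullet just above it likewise drops #5's active-treatment condition. That is plausible, but the orthostatic bullet has no cross-reference to confirm it, and either way the wording needs settling.

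Other safeguards exist. Orthostatic results go to every safety review, the investigator must see no safety concern, and the Principal Investigator and Clinical Trial Leader decide jointly. Escalation is therefore not automatic when #7 is unmet. This lowers the practical risk but does not replace a pre-specified stop.

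Three further inferences are tempting but unsupported:

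- *The safety-review checklist also points to the wrong place.* It does not. The item "Check of criteria for stopping subject treatment as per Section" 3.3.4.1 concerns individual subjects, and 3.3.4.1 holds those criteria.
- *The severe counts have different denominators (2 of 8 against 2 of 6).* They do not, since #7 names the 8-subject group. A contrast such as 50% against 34% at a 20% rate arises only if placebo events are never judged related.
- *The moderate rule in 1.4.3 is generally about twice as likely to trigger.* That needs placebo subjects to have symptoms as often as active subjects, which no document supports. Criterion #7 also counts adverse events other than orthostatic ones, which the calculation leaves out.

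**Conclusion.** The point holds as an internal inconsistency in a first-in-human stopping rule. An orthostatic stop stated without qualification in 1.4.3 is missing from the mandatory list, #7 covers only part of it, and the escalation gate refers to a section without stopping criteria. The protocol leaves four things open: whether the orthostatic rule is mandatory, which subjects count, whether relatedness is required, and whether *moderate* includes severe.

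No single figure describes the size. At an assumed 40% moderate rate on active drug, with all active cases judged related, the gap between the rules is about 23 percentage points if placebo subjects share that rate, about 3 points at 5% on placebo, and nil at 0%. Relatedness judgements can widen it. The finding rests on the text and not on these rates. It does not show that escalation would wrongly continue, and it concerns stopping escalation under 1.4.3, not ending the trial. It is more than clerical and should be corrected.

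**What to change.** Reconcile Sections 1.4.3 and 3.3.4.3 so that both state the same position on:

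- whether the orthostatic rule is a mandatory criterion, and, if it stands beside #7, that meeting either one stops escalation;
- which subjects are counted, the whole dose group or only those actively dosed;
- whether drug-relatedness is required;
- whether *moderate* includes severe.

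Which rule stands is the sponsor's decision. Separately, change the references to 3.3.4.2 for stopping criteria in Sections 1.4.3 and 3.1 so that they name the section holding those criteria. The checklist reference to 3.3.4.1 stays as it is.

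The cost is protocol wording only. Orthostatic tests are already scheduled and already part of the safety review, so no assessments, subjects or analyses are added.
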